# 2.2.2. Key Secondary Efficacy Endpoint

Mean change from Baseline through Week 16 in dysmenorrhea 2.2.3. Secondary Efficacy Endpoints Mean change from Baseline through Week 16 in dyspareunia score Mean change from Baseline through Week 16 in nonmenstrual pelvic pain Mean change from Baseline through Week 16 in dysmenorrhea Mean change from Baseline through Week 16 in dyspareunia score Mean change from Baseline through Week 16 in pill count of any rescue analgesic use Mean change from Baseline through Week 16 in opioid pill count Time to rescue medications Percentage of nonmenstrual pelvic pain responders through Week 16 Percentage of dysmenorrhea responders through Week 16 Percentage of dyspareunia responders through Week 16 Mean percentage change from Baseline through Week 16 in nonmenstrual pelvic pain Mean percentage change from Baseline through Week 16 in dysmenorrhea Mean percentage change from Baseline through Week 16 in dyspareunia Percentage of nonmenstrual pelvic pain responders through Week 16 Percentage of dysmenorrhea responders through Week 16 Percentage of dysmenorrhea responders through Week 16 Mean percentage change from Baseline through Week 16 in nonmenstrual pelvic pain Mean percentage change from Baseline through Week 16 in dysmenorrhea Mean percentage change from Baseline through Week 16 in dyspareunia Number and percentage of women who responded Mean change from Baseline through Week 16 on Number and percentage of women who responded "

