# 3.3. Determination of Sample Size

Power analysis for sample size calculation was performed under 2-sample t-test at the 5% level of significance to identify significance of the difference between MT-2990 and placebo on the mean change from Baseline through Week 16 in nonmenstrual pelvic pain. A total of 28 subjects per arm will provide at least 80% power for detecting a clinically meaningful difference (placebo versus treatment) of -0.5 in the mean change from Baseline in nonmenstrual pelvic pain and a standard deviation (SD) of 0.65,

As this study is exploratory study (proof of concept study), multiplicity for multi-endpoint is not considered. Assuming a drop-out rate of 25%, a total of 76 subjects (38 subjects per arm) are planned to be randomized in this study.

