### 8.2.1. Primary Efficacy Endpoint

[figure not shown]
Mean change from Baseline through Week 16 in nonmenstrual pelvic pain will be analyzed in table.

As the Primary analysis, Change from Baseline through Weeks 4, 8, 12, and 16 in the mean scores of nonmenstrual pelvic pain will be analyzed using a repeated measures analysis of covariance model with an unstructured covariance structure. The analysis model will include Baseline value of the endpoint and baseline value\*treatment as a covariate; weeks, treatment and weeks\*treatment as fixed effect; subjects as random effect. The Kenward-Roger approximation was used to estimate the denominator degrees of freedom. Point estimates and 95% CIs for the difference between each active dose and placebo at Week 16 and other time points will be obtained. In the event that this analysis model fail to converge, ARH(1), AR(1), CS correlation matrix will be used sequentially.

The primary efficacy analysis will be also performed on PP population.

As the secondary analysis, the primary analysis will be conducted for the primary endpoint with the last observation carried forward method for imputing the missing value at or before the Week 4, 8, 12 and 16.

[figure not shown]

Time to rescue medications is defined as the number of days from Day 1 to the first use of a rescue medication during the treatment period for patients who did not take rescue medications in the last 35 calendar days during the screening period.

Time to rescue medications will be analyzed using a log-rank test, and significance difference test based on Restricted Mean Survival Time. Same analyses will be conducted for time to hospitalization and time to surgeries.

The logistic regression model will be used to analyze the response rate (percentage) based on nonmenstrual pelvic pain . Odds ratio and risk ratios for the percentage of responders will be calculated. The analysis model will include categorization of "response" and "no response" as the dependent variable, treatment arm as the main effect, and the Baseline score for nonmenstrual pelvic pain as the covariate. This analysis will be conducted using observed case and last observation carry forward (LOCF) respectively. The last observation carried forward method will be used for the missing value at or before Week 16.

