In addition, this analysis will be conducted to dysmenorrhea pain responders and dyspareunia pain responders in the same way. And, in each responder modified by analyses will be repeated in the same way.

The plot of LS mean of change from baseline value (and SE as error bar) of dysmenorrhea and dyspareunia score will be generated.

[figure not shown]
The plot of LS mean percentage change from baseline value (and SE as error bar) of dysmenorrhea and dyspareunia score will be generated.

The ROC curve of cutoff numbers for clinical responder based on nonmenstrual pelvic pain, dysmenorrhea and dyspareunia score scale will be generated.

Responder modified by analysis use analyses will also be performed by subgroups described as below. This subgroup analysis will be performed on Week 12 and Week 16 values.

Subgroup	Category
Age	$< 25, \ge 25 \ and \le 35, > 35$
Race	American Indian or Alaska Native, Asian, Black or African
	American, Native Hawaiian or Other Pacific Islander, White, Not

	Reported, Other	
Ethnicity	Hispanic or Latino, Not Hispanic or Latino, Not Reported,	
	Unknown	
Baseline pain score for	< Median of Baseline pain score for DYS	
DYS	≥ Median of Baseline pain score for DYS	
Baseline pain score for	< Median of Baseline pain score for NMPP	
NMPP	≥ Median of Baseline pain score for NMPP	
Baseline pain score for	< Median of Baseline pain score for dyspareunia	
dyspareunia	≥ Median of Baseline pain score for dyspareunia	
Baseline analgesic use		
Time since diagnosis	$< 2, \ge 2 \ and < 5, \ge 5$	

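### Responder endpoints: add a prespecified analysis that counts discontinuation as non-response, because observed case and LOCF can both mislead if drop-out differs by arm

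*SAP*

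**What the plan says.** SAP 2.2.3 lists responder rates among the secondary efficacy endpoints, for example "Percentage of nonmenstrual pelvic pain responders through Week 16". The published text of SAP 8.2.1 sets out the method: logistic regression of response on treatment arm and Baseline score, with odds ratios and risk ratios. (The headings of the later 8.2 subsections are not visible, so this text appears under 8.2.1.)

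On missing data it says "This analysis will be conducted using observed case and last observation carry forward (LOCF) respectively", and then "The last observation carried forward method will be used for the missing value at or before Week 16". It adds that "this analysis will be conducted to dysmenorrhea pain responders and dyspareunia pain responders in the same way", and repeats the approach for a modified responder whose definition is not visible. One rule therefore governs a whole family of secondary endpoints.

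Related provisions:

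- SAP 8.2 places all efficacy analyses on the ITT population.
- Protocol 14.3.2 leaves missing-data handling to the SAP.
- SAP 3.3 plans for substantial loss: "Assuming a drop-out rate of 25%, a total of 76 subjects (38 subjects per arm) are planned to be randomized in this study".
- Protocol 7.1.1 and SAP 3.1 have women who discontinue complete the Visit 9 procedures within 10 days, or as soon as possible.
- SAP 7.3 ends each e-Diary window on the actual day of the monthly assessment.

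**The concern.** A Week 16 response rate needs a rule for women who are no longer there at Week 16. Observed case answers for stayers only, so the denominator depends on who stayed. LOCF keeps everyone with an earlier value but lets that value stand for Week 16, so a woman who improved at Week 4 and left at Week 6 can be counted as a success. Neither method, as written, counts leaving as a failure to respond.

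This affects the treatment comparison only if leaving is related to arm, and that is plausible here. Several of the withdrawal criteria in Protocol 8.5 (hypersensitivity, infusion-related reactions, blood count and liver findings) could fall more on active treatment, while leaving because pain is not relieved could fall more on placebo. At stake are the odds ratios and risk ratios for three pain domains in a proof-of-concept trial, where responder rates are easily read as the clinical result.

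**Working it through.** **The plan's own figure.** SAP 3.3 uses a two-sample t-test with difference 0.5, SD 0.65 and two-sided 5%. Exact power is 79.2% with 27 per arm and 80.7% with 28, so 28 is the smallest sufficient number. Then 28/0.75 = 37.3, rounded up to 38 per arm and 76 in total. The figure reproduces, but it is for the continuous primary endpoint; no responder rate or power is stated. At 25% drop-out, 0.25 × 76 = 19 women are left out by observed case or classified by LOCF from an earlier value.

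**Notation, per arm.** Let c be the proportion of the arm who complete and respond at Week 16, d the proportion who drop out, and q the share of leavers whose last value is a response. All three are assumptions; the documents give only d = 25% overall.

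- Leavers as non-responders: c
- Observed case: c / (1 − d)
- LOCF: c + q × d

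**Creating a difference.** Take c = 40% in both arms and the same q in both. The LOCF difference is then q × (d on MT-2990 − d on placebo).

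| Drop-out, MT-2990 / placebo | Observed case | Difference | LOCF difference, q = 0.3 to 0.7 | Leavers as non-responders |
|---|---|---|---|---|
| 25% / 25% | 53.3% vs 53.3% | 0 | 0 | 0 |
| 30% / 20% | 57.1% vs 50.0% | +7.1 points | +3 to +7 points | 0 |
| 35% / 15% | 61.5% vs 47.1% | +14.5 points | +6 to +14 points | 0 |

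The second route needs no imbalance in drop-out. With 25% drop-out in both arms but q = 0.7 on MT-2990 and 0.3 on placebo, LOCF gives 0.25 × (0.7 − 0.3) = +10 points, while observed case gives 0.

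**Hiding a difference.** Take c = 50% vs 30%, with drop-out 15% on MT-2990 and 35% on placebo. Observed case is 0.50/0.85 = 58.8% vs 0.30/0.65 = 46.2%, so 20 points become 12.7. LOCF gives 20 − 20q points: 14 at q = 0.3 and 6 at q = 0.7.

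**In whole women.** Suppose 14 of 38 leave on MT-2990 and 5 of 38 on placebo (19 of 76), with 13 completing responders in each arm.

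- Observed case: 13/24 (54%) vs 13/33 (39%), odds ratio 1.82.
- LOCF, if 7 and 1 leavers had a responding last value: 20/38 (53%) vs 14/38 (37%), odds ratio 1.90.
- Leavers as non-responders: 13/38 vs 13/38, odds ratio 1.00.

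The two planned analyses agree with each other and both differ from the third.

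**Error rates.** These come from 200,000 simulated trials per setting, with 38 per arm and a pooled two-proportion z-test at two-sided 5%, without the baseline covariate; LOCF ranges are for q = 0.5 to 0.7. With c = 35% in both arms, rejection is about 5% for all methods at 25%/25% drop-out. At 30%/20% it is 8% for observed case and 7–9% for LOCF. At 35%/15% it is 16% and 14–23%. Counting leavers as non-responders stays at 5%. With c = 55% vs 30% and drop-out 15%/35%, power is 60% with leavers as non-responders, 29% with observed case and 26–16% with LOCF.

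**Early Visit 9.** The visible text does not say whether a Visit 9 done at discontinuation sets the Week 16 assessment day. If it does, a woman whose Week 12 assessment was on Day 85 and whose early Visit 9 was on Day 100 would have a Week 16 e-Diary window of Days 86 to 100 under SAP 7.3. She would then be an observed case although she had left.

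**The case against.** **Unseen text.** The SAP contents list a response definition (7.1.2.4) and missing-data conventions (7.2). The former and the efficacy items of the latter are not in the published text. A reader might infer that the plan has no rule counting leavers as failures. The documents do not support that: such a rule could sit in either place. What can be said is that the method text names two handlings and no third. This limit stands.

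**The yardstick is a choice.** The illustrations treat leaving as non-response, so that analysis shows no error by construction. If the target is the response women would have had by staying, the picture reverses. With 50% response in both arms among stayers and leavers alike, and drop-out 35% vs 15%, observed case is correct at 50% vs 50%. Counting leavers as failures gives 0.50 × 0.65 = 32.5% vs 0.50 × 0.85 = 42.5%, a 10-point loss produced by drop-out alone. The visible text states no estimand. So it cannot be said that one method is true and the others wrong.

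**LOCF is not always off.** If no leaver's last value is a response (q = 0), LOCF classifies leavers exactly as non-responders. Deleting it, as a reader might be tempted to propose, is not justified.

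**No evidence of imbalance.** The 25% is a planning figure with no split by arm, and at 30% vs 20% the distortion is modest. This stands, and the sizes above are illustrations, not forecasts.

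**Limited reach.** These are secondary endpoints in an exploratory study without multiplicity control. The primary analysis is a repeated-measures model on the continuous score and is untouched. This stands. Having two handlings already helps, but less than it seems, because both can err in the same direction.

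**Conclusion.** The point holds as a modest, inexpensive improvement to the secondary responder analyses. In the visible text a woman who leaves is either excluded or classified by an earlier value. Relative to treating leaving as non-response, both methods can create or hide a difference when drop-out or last-value response differs by arm: about 7 points on observed case at 30% vs 20% drop-out, and about 14 at 35% vs 15%, with 40% composite response assumed in both arms. With equal drop-out and equal last-value response neither creates a difference where the composite has none; both only raise the reported rates.

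A reader might go further and infer that the responder comparison is biased as planned, or that any drop-out distorts it. The documents do not support this, because it needs an imbalance by arm that they neither state nor rule out.

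**What to change.** Add to SAP 8.2.1, before database lock, a responder analysis on all ITT subjects in the same baseline-adjusted logistic model, for each responder endpoint, in which no Week 16 value because of discontinuation counts as non-response. Report it alongside observed case and LOCF, both kept as supportive.

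State two further points:

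- An early Visit 9 done at discontinuation does not count as an observed Week 16 response in this analysis.
- How a missing Week 16 value is handled in a woman who did not discontinue.

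If the unpublished parts of SAP 7.1.2.4 or 7.2 already contain such a rule, a cross-reference from 8.2.1 is enough.

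The change needs SAP wording and one extra derivation, with no new data, visits or subjects. The price is in interpretation. Reported rates fall clearly in both arms (from 62% and 47% to 40% and 40% in the 35%/15% illustration), and the result is a composite in which drop-out itself counts as failure. The report should say so.

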#### 6.2. Statistical Tests

Unless otherwise specified, all formal statistical tests of treatment effects will be done at two-sided significance level of 0.05. Point estimates will be accompanied with two-sided 95% confidence intervals where applicable.

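### The responder subgroup analyses in SAP 8.2 show no treatment-by-subgroup term, so as written they do not test whether the effect differs between subgroups, and any within-level p-values would be easy to over-read

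*SAP*

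**What the plan says.** The last paragraph and table of SAP 8.2, just before 8.3, state that the modified-responder "analyses will also be performed by subgroups described as below. This subgroup analysis will be performed on Week 12 and Week 16 values". The table lists eight factors: age (3 levels), race (7), ethnicity (4), baseline dysmenorrhea, nonmenstrual pelvic pain and dyspareunia (each split at its median), baseline analgesic use (levels not visible) and time since diagnosis (3).

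The responder method is set out a little earlier, under 8.2.1. It is a logistic regression with "treatment arm as the main effect, and the Baseline score for nonmenstrual pelvic pain as the covariate", giving odds ratios and risk ratios, by observed case and by LOCF. It is carried over to dysmenorrhea and dyspareunia responders, and to the modified definition.

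Two general rules bear on this. SAP 6.2 says that, unless otherwise specified, "all formal statistical tests of treatment effects will be done at two-sided significance level of 0.05". SAP 3.3 calls the study exploratory and says that "multiplicity for multi-endpoint is not considered".

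**The concern.** The question for a subgroup analysis is whether the treatment effect differs between levels. Rerunning a treatment-plus-baseline model inside each level does not answer it. A significant result in one half and a non-significant one in the other can arise by chance from identical true effects. The authors write interactions out where they want them: the primary model in 8.2.1 has baseline-by-treatment and week-by-treatment terms. The visible responder model has none.

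In a proof-of-concept trial, an apparently responsive subgroup could influence whom a later trial enrols. The plan as written offers no test of whether such a subgroup differs from the rest, and the visible text does not say that within-level results are descriptive.

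**Working it through.** **Sample size (the plan's own figure).** SAP 3.3: "A total of 28 subjects per arm will provide at least 80% power" for a "difference (placebo versus treatment) of -0.5 in the mean change from Baseline in nonmenstrual pelvic pain and a standard deviation (SD) of 0.65". An exact two-sample t-test at two-sided 5% needs 27.52, so 28 per arm, with power 80.7%. Dropout: 28 / (1 − 0.25) = 37.3, so 38 per arm and 76 in all. The figure reproduces. A median split therefore gives 76 / 2 = 38 women per half, or about 28 per half if only 2 × 28 = 56 are observed.

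**Number of level analyses.** Visible levels: 3 + 7 + 4 + (3 × 2) + 3 = 23. Assuming two levels for baseline analgesic use gives 25. Over two visits that is 50 per responder endpoint. If independent, the chance of at least one p < 0.05 would be 1 − 0.95^50 = 92.3%. This overstates the risk: the factors divide the same women, the visits are correlated, and many race and ethnicity levels will be too small to fit.

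**Restricted check.** To leave sparse cells out, take only the three median splits (6 levels). The independence reference is 1 − 0.95^6 = 26.5% at one visit and 1 − 0.95^12 = 46.0% at two. Simulation allows for the overlap. Its assumptions, none given in the documents, are no drug effect, 38 women per arm, response rate 30–50%, and latent correlation 0.8 between visits and 0.5 between endpoints. Each level gets a Wald test of the log odds ratio.

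| Within-level tests, three median splits, N = 76 | At least one p < 0.05 |
|---|---|
| One endpoint, one visit | about 17–18% |
| One endpoint, both visits | about 28–30% |
| Three endpoints, both visits | about 59–63% |

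Separate runs put the first row between 17% and 20%. With 56 women it is 14–17%. In nearly all the one-endpoint, one-visit false positives, one half was significant and the other was not.

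**All eight factors.** A simulation that kept the baseline covariate, used an assumed subgroup mix and dropped levels that could not be fitted gave 24–39% for one endpoint at one visit and 37–60% over both visits (N = 56–76, visit correlation 0.6–0.9).

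**What an interaction test would do.** Three independent tests give 1 − 0.95^3 = 14.3%. Simulated at Week 16, at least one of the three median-split interactions has p < 0.05 in 13–14% of null trials for one endpoint and 32–35% for three endpoints. The test asks the right question but reduces chance findings only modestly.

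**Its power.** If the whole-trial log odds ratio has variance V, each half has about 2V and the difference between halves about 4V, so the standard error doubles. At an assumed 40% response, V = 2 / (38 × 0.4 × 0.6) = 0.219, SE = 0.468 and the interaction SE is about 0.94. At 80% power the detectable difference is roughly (1.96 + 0.84) × 0.94 = 2.6 on the log scale, a ratio of odds ratios of about 14.

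**The case against.** A reader might infer that the SAP orders a formal 5% test in every level. It does not say so. The subgroup paragraph mentions no p-value, test or alpha. SAP 6.2 sets the level for formal tests without saying that every analysis is one, and the responder model is described as yielding odds and risk ratios. A table of estimates with intervals would fit the wording. This stands, so the error rates above apply only if within-level p-values are reported.

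A reader might also infer that a false subgroup finding is likely. For one endpoint and the median splits it is not: 17–18% at one visit and 28–30% over both. The figure passes one half clearly only when counting over three endpoints, and SAP 3.3 openly waives multiplicity across endpoints. That waiver does not mention subgroups or visits, but it is a reason not to lead with 59–63%.

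The SAP contents list sections 8.2.1 to 8.2.4, while only the 8.2.1 heading is visible. The subgroup paragraph comes last and may sit under a removed heading that labels it exploratory. This cannot be excluded. Nor is the choice of visit wholly open, since SAP 3.1 places the primary and secondary endpoints at Week 16 and end of treatment at Week 12.

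Finally, no visible objective, endpoint or decision rule depends on subgroups. That limits the severity. It does not supply the missing interaction term.

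**Conclusion.** The point holds in limited form and is minor. On the visible text, the responder subgroup analyses use a model without a treatment-by-subgroup term and so do not test for a difference in effect. If within-level p-values are shown at 5%, the three median splits alone produce a nominally significant level by chance in about 17–18% of null trials for one endpoint at one visit and about 28–30% over both visits. The rate is about 59–63% across three endpoints at both visits, with the waiver in SAP 3.3 noted. These figures rest on 76 women, an assumed response rate of 30–50%, visit correlation 0.8 and, for three endpoints, endpoint correlation 0.5.

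The documents do not support a claim that every level is formally tested, that 92.3% is the real error rate, or that the trial's main conclusion is at risk. The primary analysis and sample size are untouched.

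**What to change.** In SAP 8.2, for each factor with enough women per level (for example the median splits, age and time since diagnosis), fit one responder model on all women with treatment, baseline score, subgroup and treatment-by-subgroup. Collapse sparse race and ethnicity levels or describe them only, because a full interaction model with seven or four levels will probably not be estimable with 76 women. Report the Week 16 interaction p-value, labelled exploratory and not adjusted for multiplicity. Show within-level odds ratios with 95% confidence intervals as description, without significance claims, and present Week 12 as supportive. If a removed heading already labels the section exploratory, only the interaction term and the rule on within-level claims need adding.

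The cost is SAP wording and a small change to the table programs, with no new data. The drawback is low power for interactions at this size, together with some remaining chance findings (about 13–14% for three splits and one endpoint). The descriptive labelling is therefore needed as well as the interaction term.
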